9.1.5.	Study Files and Retention of Records	56
9.1.6.	Case Report Forms	56
9.1.7.	Inspections	57
9.1.8.	Protocol Compliance	57
9.2.	Sponsor Responsibilities.....	57
9.2.1.	Protocol Modifications	57
9.2.2.	Access to Information for Monitoring, Auditing or Inspections	57
9.2.3.	Study Report and Publications.....	57
10.	END OF STUDY CRITERIA	59
10.1.	Completion of the Study	59
10.2.	Subject Discontinuation.....	59
10.3.	Study Termination	59
11.	REFERENCES	61
12.	APPENDICES	63
Appendix 1.	Sponsor-Investigator Signature Page.....	64
Appendix 2.	Schedule of Events Table	65
Appendix 3.	Investigator’s Global Assessment (IGA).....	68
Appendix 4.	Common Terminology Criteria for Adverse Events (CTCAE) V. 5.0.....	69
Appendix 5.	Acne Specific Quality of Life (QoL) Questionnaire	70

PROTOCOL SYNOPSIS
Naked Biome, Inc.
[name]
[name]

Study Title: A Multicenter, Randomized, Double-Blind, Vehicle-Controlled Phase 1B Study of the Safety, Short-Term Engraftment and Action of NB01 in Adults with Moderate Acne

IND Number: 17552
EudraCT Number: Not Applicable
Clinical Trials.gov Identifier: NCT03709654

Study Centers Planned: Approximately three study centers in the US.

Objectives: The objectives of this study are as follows:

1. Primary
 1. To determine the safety and tolerability of a multiple application of topical *Propionibacterium acnes* (*P. acnes*) microbiome transplant (“NB01”).
2. Exploratory
 1. To define engraftment duration of NB01.
 2. To evaluate preliminary clinical efficacy using Acne Lesion Counts (total, inflammatory, and non-inflammatory), Investigator Global Assessment (IGA) and subjective improvement on acne based on subject reported outcomes (Acne QoL Questionnaire).
 3. To evaluate treatment effects, based sebum production in a subpopulation from sites 02 and 03.

Study Design: Multicenter, Randomized, Double-Blind, Vehicle-Controlled, Phase 1B Study

No. of Subjects: 36

Target Population: Adult Male and Female Subjects with Moderate Facial Acne Vulgaris

Duration of Subject Participation: Subject participation will be approximately four months. Study duration will be approximately one year.

Diagnosis and Main Eligibility Criteria:

Inclusion Criteria

1. Subject has provided written informed consent.
2. Subject is male or non-pregnant female, 18-40 years of age, inclusive at Screening.
3. Subject has a clinical diagnosis of moderate facial acne vulgaris defined as Grade 3 on the IGA (see [Appendix 3](#), IGA Grading).

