- Local urine pregnancy test (Screening, Day 1, and Week 12/EOT only)
- Twice daily facial washing
- BPO pre-treatment of at least 5, but no more than 7, consecutive days (Screening). Should a subject require a modified Screening period schedule, BPO may be applied for more than 7 days with prior approval of the Sponsor Medical Monitor.
- Subject Diary completion for pre-treatment period BPO and facial washing (Screening)
- Subject Diary completion for study drug application (Day 1 through Week 12/EOT), facial washing (Day 1 through Week 12/EOT), and LSRs (Day 1 through Week 16/EOS)
- Assessment of adverse events (AEs) and local skin reactions (LSRs)
- Review of concomitant medications
- IGA (Day 1 through Week 12/EOT)
- Acne lesion counts, including inflammatory and non-inflammatory lesion counts (Day 1 through Week 12/EOT)
- Optional photography (Day 1 through Week 12/EOT)
- Sebum production measurements (Day 1 through Week 12/EOT)
- Acne Quality of Life (QoL) questionnaire (Day 1 through Week 12/EOT)
- Obtain facial samples for TaqMan® engraftment assay
 - Cheek Swab, skin surface (Day 1 through Week 12/EOT)
 - Biore® Strip, follicular (Screening, and Week 12/EOT only)
- Study drug application (Day 1 through end of Week 11*)

*Subjects must complete application of study drug at least 3 days prior to, but no more than 7 days from, the Week 12 visit.

See [Appendix 2](#) for additional details in the Schedule of Events table.

Test Product, Dose, and Mode of Administration:

NB01 is a topical live biologic. The active pharmaceutical ingredient consists of a single strain of health-associated *P. acnes* bacterium in a cryopreservative (glycerol), water and phosphate buffered saline (PBS). Vehicle-control consists of glycerol, water and PBS. Both NB01 and vehicle-control are delivered topically in single-dosed vacuum-sealed pads.

Study Measurements:

The following assessments will be completed for each subject according to the Schedule of Events (see [Appendix 2](#)).

Dosing Compliance: Measures of study drug compliance will include the duration (days) of treatment (defined as last dose date – first dose date +1), the total number of applications (determined from the doses reported in the Subject Diary), and the percent of expected doses applied. Subjects who apply at least 80% of the expected total number of applications and have no other evidence of material dosing non-compliance will be considered to be compliant with study drug dosing.

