3.3. Study Design

This is a multicenter, randomized, double-blind, vehicle-controlled Phase 1B study of daily doses of topically-delivered NB01 or vehicle-control in subjects with moderate, non-cyclical facial acne.

Subjects who consent to participate in the study will initiate Screening procedures, during which they will be pre-treated with 5% topical BPO gel once daily (QD) for 5 to 7 days before randomizing into the study. Subjects with modified screening period schedules may be able to apply BPO for more than 7 days; however, this must be pre-approved by the Sponsor’s Medical Monitor.

Thirty six subjects were randomized into the study to receive high-dose NB01 (10^5 CFU/cm²) or vehicle-control.

Subjects will be stratified according to these variables:

- Sex (male/female)
- Age (18-25 years old/26-40 years old)

The study will comprise of subjects with moderate facial acne who will be randomized to one of two treatment arms, either vehicle-control or high-dose NB01.

The study arms consist of vehicle-control control and daily high-dose (10^5 CFU/cm²) NB01, with subjects enrolled at a 2:1 ratio (treatment arm to vehicle-control arm). The PI may employ a dose reduction strategy with approval from the Sponsor's Medical Monitor to reduce/modify dosing based on individual subject's tolerability. Such changes, however, shall not be made without the written approval of the Medical Monitor, see [Section 7.4](#).

Subjects will remain on study through 11 weeks of study treatment.

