Non-systemic (local) AEs Grade 3 or higher for which there is no clear alternative explanation of the cause of the AE will also be considered DLTs. Any subject who experiences a DLT, as described above, must discontinue treatment and be scheduled for a final visit. Any DLTs that are Grade 2 or greater systemic AEs must be reported by the PI immediately. If three or more subjects experience DLTs in the study, enrollment in the study will be halted, and a safety review will occur using an independent medical reviewer who will have access to the subject's treatment allocation. This review shall be completed promptly within 10 business days. Subjects who are active in the study will be instructed to withhold study drug applications during the safety review period. If all of the subjects experiencing DLTs (i.e. three or more) are found to be subjects receiving the active NB01 study drug, the independent medical reviewer will provide a written recommendation to the Sponsor to continue the study, discontinue the study or modify the study protocol. The Sponsor is responsible for promptly reviewing the independent medical reviewer's recommendations, accepting or rejecting these recommendations, and determining whether amendments to the protocol or changes in study conduct will be required. The Sponsor will provide the final written decision regarding the study status. In the event this is not the case, the independent medical reviewer will notify the Sponsor and Medical Monitor of how many subject's DLTs were in subjects receiving vehicle (e.g. Y subjects). In the event Y new subjects experience DLTs, the independent medical reviewer review process outlined above will be repeated. This process will be repeated throughout the entire study until the study is complete or

the stopping rule has been met. In the event that a total of three (3) or more subjects experience DLTs related to NB01 study drug, the study will be discontinued.

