7.4. Toxicity Management

A dose mitigation strategy will be employed whereby, with Medical Monitor approval, the dose may be reduced/modified according to the individual subject's tolerance. Typical modification may include short drug holiday periods off therapy, every other day dosing, etc. Such changes however shall not be made without the written approval of the Medical Monitor.

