8.2 Analysis Populations

8.2.1 *Safety Population*

The Safety population will include all randomized subjects who received and applied study drug. Subjects will have their first application of test article applied in the clinic by the PI (or sub-I-designee) during their Baseline Visit on Day 1. Subjects will be included in a treatment group based on the treatment they received (even if not the treatment group to which they were randomized). If a subject administered more than one type of test article during the trial, then the subject will be included in the treatment group to which they were randomized.

8.2.2 *Modified Intent-to-Treat Population*

The modified intent-to-treat (mITT) population will include all randomized subjects who were dispensed the study drug and have at least one post-baseline assessment. Subjects will be included in the treatment group to which they were randomized, regardless of the treatment received.

8.2.3 *Per-Protocol Population*

The per-protocol (PP) population will include a subset of the mITT population who completed the study without significant protocol deviations (as will be determined prior to unblinding the randomization) and met the criteria as specified below. Subjects will be included in the treatment group based on the treatment received.

- Meets all inclusion criteria and does not meet exclusion criteria #1-11 and #13-22.
- Has not taken or applied any interfering concomitant medications/therapies.
- Completed Visit 5/EOT procedures on Days 71 to 90 with the visit occurring 1 to 10 days after the final application of test article.
- Applied at least 80% of the expected doses with no other evidence of material dosing non-compliance.

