8.8 Dosing Compliance

Subjects who consent to participate in the study are to apply 5% topical BPO gel QD for 5 to 7 days prior to randomization at the Baseline visit (Day 1). The number of days of BPO dosing and the number of doses applied during the screening period will be tabulated by treatment group and overall for the mITT and PP populations. The proportion of subjects compliant with BPO dosing will also be tabulated where compliance is defined as at least 5 days of BPO application during the week prior to Day 1 with the last BPO application occurring 24-48 hours prior to Day 1 and no BPO application within approximately 24 hours of the Day 1 visit.

Descriptive statistics will be used to summarize for each treatment group the duration (days) of treatment (defined as last dose date – first dose date +1), the total number of applications (determined from the doses reported in the Subject Diary), and the percent of expected doses applied for the mITT and PP populations. The protocol specifies that a subject will dose each evening for 11 weeks for a total of 77 doses. Visit 5/EOT is expected to occur 3 to 7 days after the last dose is applied, therefore, the final dose should be applied between Study Days 73 to 77, inclusive. Accordingly, the percent of expected doses applied by a subject will use 75 doses as the denominator. Subjects who apply at least 80% of the expected total number of applications and have no other evidence of material dosing non-compliance will be considered to be compliant with study drug dosing.

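### The fixed 75-dose denominator can label subjects on approved or mandated dose modifications non-compliant and outside PP, and no planned output counts those modifications by arm

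*Protocol*

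**What the plan says.** **Modifications and holds.** Protocol 3.3 states: "The PI may employ a dose reduction strategy with approval from the Sponsor's Medical Monitor to reduce/modify dosing". Section 7.4 requires the Medical Monitor's written approval and gives examples: "Typical modification may include short drug holiday periods off therapy, every other day dosing, etc". Under 7.2.1, three or more subjects with dose-limiting toxicities (DLTs) trigger an independent review, to be finished within 10 business days, and "Subjects who are active in the study will be instructed to withhold study drug applications during the safety review period". The same section halts dosing of active subjects during a review, of up to 5 business days, of a serious adverse event judged at least possibly related.

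**Compliance and PP.** The Protocol synopsis, 3.1.1 and 8.4.1 classify as compliant "Subjects who apply at least 80% of the expected total number of applications and have no other evidence of material dosing non-compliance", without defining the expected number. SAP 8.8 supplies it. It starts from the premise that "a subject will dose each evening for 11 weeks for a total of 77 doses", allows for a last dose on Days 73 to 77, and concludes that "the percent of expected doses applied by a subject will use 75 doses as the denominator". SAP 8.2.3 lists among its PP conditions: "Applied at least 80% of the expected doses with no other evidence of material dosing non-compliance". The Protocol's own PP definition (8.2.3) refers only to completing the study without significant deviations, so the link from dose count to PP membership is made in the SAP.

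**Tolerability.** The primary objective opens "To determine the safety and tolerability of a multiple application of topical". The safety outputs are in SAP 8.12, with disposition and deviations in SAP 8.6.

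**The concern.** Two parts of the plan do not fit together. One lets dosing be reduced or suspended by instruction. The other scores every subject against the same number of doses, whatever the instruction was. A dose withheld with written approval, or by order during a safety review, then counts exactly like a dose the subject forgot. A subject can do everything asked and still be reported as non-compliant and be left out of PP.

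The second issue is what gets reported. The number of subjects in each arm who could not stay on the planned daily regimen is a direct measure of tolerability. If the plan shows those doses only as lower compliance or lower exposure, the reader of the study report cannot separate intolerance from poor adherence.

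**Working it through.** **Inputs.** 77 scheduled doses, last dose on Days 73 to 77, denominator 75 (SAP 8.8); 80% rule (Protocol 3.1.1; SAP 8.2.3 and 8.8); Visit 5 target Day 80, 3 to 7 days after the last dose (schedule of events); DLT review of at most 10 business days, taken here as 14 calendar days (Protocol 7.2.1); 36 subjects at 2:1 (Protocol 3.3), nominally 24 NB01 and 12 vehicle.

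**Reproducing the SAP's figure.** 11 × 7 = 77. Day 80 − 7 = 73 and 80 − 3 = 77; the midpoint is 75, which matches SAP 8.8.

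**Cut-off.** 0.80 × 75 = 60 doses.

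**Doses for a subject who follows every instruction.** Let T be the last day on which a dose may fall.

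- Holiday or hold of h days: T − h doses. It stays at or above 60 if h ≤ T − 60.
- Daily through Day k, then every other day to the end: k + floor((T − k)/2) doses.

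| T | Missed doses tolerated | 7-day holiday | 14-day hold | Every other day after Day 8 | Every other day after Day 43 | Smallest k reaching 60 |
|---|---|---|---|---|---|---|
| 73 | 13 | 66 (88.0%) | 59 (78.7%) | 40 (53.3%) | 58 (77.3%) | 47 |
| 75 | 15 | 68 (90.7%) | 61 (81.3%) | 41 (54.7%) | 59 (78.7%) | 45 |
| 77 | 17 | 70 (93.3%) | 63 (84.0%) | 42 (56.0%) | 60 (80.0%) | 43 |

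For example, k = 8 and T = 75 gives 8 + floor(67/2) = 8 + 33 = 41. For k = 43 it is 43 + 16 = 59.

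A short holiday therefore passes. Sustained every-other-day dosing passes only if daily dosing ran to about Day 43 to 47. A full 14-day hold fails only for a last dose on Day 73 (59/75); at Day 74 it gives exactly 60. Against instructed doses, the subject with 41 applications would score 41/41 = 100%.

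**What the planned outputs show about modifications.**

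- SAP 8.6: study withdrawals with reasons, and protocol deviations by type. An approved modification follows the Protocol, so it need not appear as a deviation.
- SAP 8.12.1: total use from days applied, with no reason for days not applied.
- SAP 8.12.2: adverse events by class, term, severity and relationship, plus DLT and serious-event summaries. The listing names no item for action taken with study drug.
- SAP 8.12.3: local skin reactions by visit, and weekly from diaries. These show the reactions, not the dosing response to them.
- Under SAP 7.2, a skin reaction that leads to withholding becomes an adverse event. So does one that needs medical intervention or spreads beyond the treatment area, and no table separates these routes.

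None of these gives a count by arm of subjects whose dosing was interrupted or reduced for intolerance.

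**Scale.** The documents state no modification rate. With 24 NB01 subjects, 2 to 4 modified subjects would be 2/24 = 8% to 4/24 = 17% of the arm. If, purely as an assumption, 5% to 30% fell below 60 doses, the expected loss from the NB01 PP set would be 24 × 0.05 = 1.2 to 24 × 0.30 = 7.2 subjects.

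**The case against.** The strongest reply is that a PP set is meant to contain adequately exposed subjects, so a fixed dose requirement is a normal design choice. The Safety and modified intent-to-treat sets keep everyone concerned, every primary safety analysis uses the Safety population, and PP feeds only exploratory comparisons in a study with no formal sample size. Much of the intolerance is also captured elsewhere: weekly diary scores record the worst severity of each skin reaction in the week it occurred, reactions that lead to withholding enter the adverse event tables, and DLTs and withdrawals are tabulated by arm.

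All of that stands, and it limits the point. It does not justify calling an obedient subject non-compliant, and it does not supply the missing count. Wanting adequate exposure in PP is a reason to name the criterion as exposure, not compliance.

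Several stronger readings are tempting but unsupported:

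- *Any approved modification removes the subject from PP.* It does not; up to 13 to 17 missed doses are tolerated. The additional, undefined test for other material non-compliance could be applied to such a subject, but nothing says it will be.
- *The NB01 PP arm becomes a set of tolerators while vehicle is untouched.* The documents give no modification rate for either arm, and the 7.2.1 holds apply to all active subjects in both.
- *Reduced dosing hides intolerance in the skin reaction tables.* The size of any such dilution would have to be invented, the weekly diary tables still show earlier peaks, and at Week 12 everyone has been off drug for 3 to 7 days. Splitting those tables by regimen would give sparse cells confounded by the intolerance itself.
- *Schedule footnote k removes the Day 8 and Day 43 doses as well.* The study drug application row marks both visits, so the footnote cannot safely be counted that way.

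**Conclusion.** The point holds in a limited form. The SAP's fixed denominator has no allowance for approved or mandated withholding. As a result, sustained every-other-day dosing begun before about Day 43 to 47, or a full 14-day hold with a last dose on Day 73, can put a fully obedient subject below 60 doses, with a non-compliant label and exclusion from PP. The effect on PP is confined to exploratory analyses. Its size and direction between arms cannot be stated from the documents.

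The reporting gap matters more: tolerability is part of the primary objective, and no output shows how many subjects per arm had dosing reduced or interrupted for intolerance.

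The dose counts assume that no other doses are missed, that every-other-day dosing continues to the end of treatment, and that 10 business days is 14 calendar days. The dose-modification passages (Protocol 3.3, 7.2.1, 7.4) and the compliance and PP passages (Protocol 3.1.1 and 8.4.1; SAP 8.2.3 and 8.8) need to be reconciled. Nothing here bears on which dosing rule is right.

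**What to change.** 1. In SAP 8.8, report compliance against the doses the subject was instructed to apply, leaving out of the expected count those withheld under an approved 7.4 modification or a 7.2.1 hold. Report percent of the 75 planned doses separately, as exposure.
2. In SAP 8.2.3, state which of the two figures the 80% rule uses, and run the other as a sensitivity PP set. Either choice is defensible: the first admits some subjects with lower exposure, the second excludes some who followed instructions. Settle it before the initial freeze described in SAP 8.3, when populations are identified and the project statistician is unblinded.
3. In SAP 8.12, add a table by arm in the Safety population of subjects with any interruption, reduction or permanent stop of study drug for intolerance, with exact 95% confidence intervals.

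The cost is SAP wording, one derived variable built from Medical Monitor approvals and diary dates, and one or two tables. The documents do not say whether those approvals are held in the database; if not, the written approvals would have to be transcribed. No dosing rule changes.

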1. INTRODUCTION

1.1. Background

Naked Biome hypothesizes that eliminating resident disease-associated bacterial strains and replacing them with a health-associated *Propionibacterium acnes* (*P. acnes*) transplant may help to improve, mitigate, treat, or prevent acne flares. In a Phase I single application study of NB01 conducted by the Sponsor, all 10 subjects completed the study without any drug-related adverse events (AEs).

Genotypic and phenotypic work performed by the Sponsor has identified candidate strains sourced from healthy subjects that match all our criteria for health as defined by the literature. Genotypically, the Sponsor's candidate strain is a *P. acnes* ribotype 2, deoR+ (Johnson et al. 2016), lipase type II+ (Tomida et al. 2013) which contains a complete CRISPR system (Johnson et al. 2016), does not contain the pIMPLE plasmid (Kasimatis et al. 2013), and has no identifiable genomic evidence of antibiotic resistance. Phenotypically, the candidate strain produces low levels of porphyrin, comparable to other healthy associated ribotype 2's in the literature and is sensitive to all five antibiotics tested internally (Clindamycin, Doxycycline, Erythromycin, Minocycline, Tetracycline as was measured with Etest [bioMérieux]).

Additional safety assessments were performed by CHR-Hansen, Naked Biome's GMP manufacturer, who confirmed that no genomic antibiotic resistance genes were present and that the candidate strain was sensitive to 13 out of 14 tested antibiotics, resistant only to metronidazole which *P. acnes* has known natural resistance to and was additionally non-hemolytic and non-cytotoxic.

Outside of known association of *P. acnes* with acne vulgaris, below is an accrued list of rare opportunistic infections associated with *P. acnes*. *P. acnes* has been observed in other infections such as implant-associated, soft tissue, periodontal, periocular, cardiovascular system, and deep-organ tissues infections, and may also have a role in relation to pulmonary infection as the bacteria can be isolated from lungs and lymph nodes. Routes of infection are often from the subject's own commensal flora (normal skin or oral tract) (Kwon and Suh 2016). The expanded multi-locus sequence typing scheme based on 7 housekeeping genes and 2 putative virulence genes developed by McDowell et al gives a good resolution and revealed strains which seem to have an increased capacity to cause infections and others that are rarer or found mainly among healthy individuals (McDowell et al. 2012, McDowell et al. 2013).

Strain HP4G1 has a deoR repressor gene just upstream of the porphyrin operon suggesting a mechanism for reduced porphyrin synthesis and thus may not be associated with acne vulgaris. Further, the strain has a PAp60/PAmce allele combination found in non-invasive *P. acnes* strains and lacks 2 of 4 genes involved in iron uptake, which is of importance for growth in the human body at conditions with low iron access. Notably, regarding CAMP factors 1-4, which are expected to be involved in pathogenicity and are involved in co-hemolysin with *Staphylococcus aureus* (*S. aureus*), HP4G1 had a mutation in the CAMP 2

gene leading to an extension of the gene as the stop codon was interrupted. This variant has not been observed before and as CAMP factor 2 is described as having properties for co-hemolysin and exotoxin, this may lower the pathogenic potential of the strain. Moreover, the strains belong to the CC72 clonal complex which, compared to CC5, contains strains less commonly isolated from healthy humans or individuals with infections. HP4G1 was found to be a ST100-like type not previously reported and most likely has a non-functional CAMP2 gene due to a mutation in the stop codon. Therefore, HP4G1 is most likely less virulent than *P. acnes* in general with a low risk of causing infections.

Prophyrin is a known inflammatory metabolite involved in the pathogenesis of acne. Prophyrin is produced by the *P. acnes* bacterium and is a photosensitizing agent. Dermatologists routinely use blue and red-light therapies to selectively target *P. acnes*-produced coproporphyrin III and protoporphyrin IX, respectively, thereby eliminating *P. acnes* and improving disease. As stated above, HP4G1 has a repressor of porphyrin production, called deoR. *In vivo*, the HP4G1 strain produces less porphyrin than acne-associated strains that lack the deoR repressor operon. Despite that, the HP4G1 strain is a low porphyrin producer; the fact that it is applied in significant quantities (10^5 CFU/cm²) could lead to a temporary increase in porphyrin upon application. This hypothetical increase could be photosensitizing to subjects, as such, photosensitivity has been included as a theoretical side effect of HP4G1 application.

The Sponsor intends to address the risk of these opportunistic infections through the selection of genotypic and phenotypic characteristics most associated with health and with the implementation of appropriate exclusion criteria to eliminate subjects that may have increased risk of a *P. acnes* infection.

P. acnes is most specific to facial pilosebaceous region which is the natural niche for *P. acnes*, and therefore the best region for application to appropriate the sensitivity and therapeutic impact of a topical *P. acnes* transplant (McGinley et al. 1980).

